Respiratory pressures and diaphragm electromyography (EMGdi). An esophageal electrodeballoon catheter will be inserted nasally and positioned as previously described (30,71). EMGdi will be recorded continuously using an esophageal electrode catheter consisting of 5 electrode pairs at rest and during exercise and analyzed as previously described (34-36). The raw EMGdi signal will be sampled at 2000 Hz (PowerLab, model ML880; ADInstruments, CastleHill, NSW, Australia), band-pass filtered between 20-1000 Hz (Bioamplifier model RA-8; Guanzhou Yinghui Medical Equipment Co. Ltd. Guangzhou, China) and converted to a root mean square (RMS) using computer software (Chart v5.4, ADInstruments). For each breath, the data from the electrode pair with the largest value from the five electrode pairs will be used for analysis. Maximal EMGdi (EMGdi,max) will be determined from IC maneuvers (72). EMGdi/EMGdi, max will be used as an index of the inspiratory neural drive to the crural diaphragm (30-33). Esophageal (Pes) and gastric pressures (Pga) will be recorded continuously at a rate of 200 Hz (PowerLab); transdiaphragmatic pressure (Pdi) will be recorded as the difference between Pga and Pes signals. The continuous flow signal from the Vmax229d system will be input into the PowerLab system for offline analysis. Pre- and post-exercise inspiratory sniffs will be performed to obtain maximum Pes (Pes,sn) and Pdi (Pdi,sn). IC maneuvers at rest and throughout exercise will be used to obtain dynamic peak inspiratory Pes (Pes,IC) and Pdi (Pdi,IC). Pre- and post-exercise FVC maneuvers will also performed to obtain dynamic peak expiratory Pes (Pes,FVC). Respiratory mechanics will be analyzed as previously described (34-36).

Statistical analysis: A sample size of 17 will provide at least 80% power to detect a clinically significant treatment difference of 1 Borg unit in dyspnea intensity at a standardized time during constant work-rate exercise (i.e., at the end of the 4-min exercise test). This sample size estimation is based on the following assumptions: a standard deviation of 1.35 Borg units for the difference between values in a two-treatment crossover study [Appendix 3] (37,40), α =0.05, β =0.8, and a two-tailed test of significance. A p<0.05 significance level will be used for all statistical analyses.

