Paired *t*-tests with appropriate Bonferroni adjustments for multiple comparisons will be used to compare treatment responses, i.e., post-dose responses to fentanyl citrate versus bronchodilator. Comparisons will be made for: 1) resting pulmonary function; 2) cardiorespiratory (e.g., V_E, V_T, breathing frequency, HR, etc.), respiratory mechanical (e.g., IC, inspiratory reserve volume (IRV)), metabolic and gas exchange (e.g., VO₂, carbon dioxide output (VCO₂), end-tidal CO₂ (P_{ET}CO₂), SpO₂), and perceptual (e.g., intensity of dyspnea and leg discomfort) responses measured at rest, isotime and end-exercise; 3) Pes, Pga and Pdi-derived measurements of respiratory mechanics and muscle recruitment patterns; 4) EMGdi-derived indices of inspiratory neural drive (e.g., EMGdi/EMGdi,max). Descriptors of dyspnea at end-exercise and reasons for stopping exercise will be analyzed as frequency statistics and compared between-groups and between-treatments using Fisher's exact test.

To identify contributors to exertional dyspnea intensity (and its qualitative and affective dimensions), Pearson correlations will be used to establish associations between intra-subject treatment differences (i.e., post- minus pre-treatment) in isotime (4-min) measurements of exertional dyspnea intensity and relevant independent variables which will include: concurrent differences in cardiorespiratory and dynamic respiratory mechanical measurements at isotime during exercise; differences in resting lung function measurements, and; various baseline characteristics (possible

covariates). A multivariable linear regression model will be used to further evaluate the relationship between dyspnea intensity and any significant variables: treatment will be included as a categorical effect, an interaction term will be used to determine whether the relationship was similar across treatments (independent variable*treatment), and subjects will be treated as random effects to account for serial measurements (subject nested within treatment).

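### An open list of candidate contributors to dyspnea is screened by Pearson correlation at an unadjusted p<0.05, and the variables that pass are refitted on the same 17 patients, so chance associations can be reported as contributors

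*Combined protocol and SAP*

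**What the plan says.** All references are to the Statistical analysis section under METHODS in the combined protocol and SAP.

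- One threshold applies throughout: "A p<0.05 significance level will be used for all statistical analyses".
- Multiplicity control appears once, for the paired t-tests of post-dose values: "appropriate Bonferroni adjustments for multiple comparisons will be used to compare treatment responses".
- A separate paragraph sets out the search for contributors to dyspnea intensity and to its qualitative and affective dimensions. There, "Pearson correlations will be used to establish associations between intra-subject treatment differences", defined as post- minus pre-treatment values at 4 minutes, and three classes of variable: changes in cardiorespiratory and dynamic mechanical measurements, changes in resting lung function, and baseline characteristics. No list, count or adjustment is given.
- A multivariable regression is then used to "further evaluate the relationship between dyspnea intensity and any significant variables". It includes treatment, a variable-by-treatment interaction and random subject effects.

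The plan gives this search no exploratory label, hold-out sample, cross-validation or shrinkage. It also does not say whether the correlations are run within each treatment (17 pairs) or on both treatments together (34 rows).

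**The concern.** The section's wording aims to identify contributors and establish associations, and the section on anticipated results expects a physiological rationale for combining treatments. A variable that passes the screen may therefore be read as a mechanism.

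Three features work against that reading. Many tests at 0.05 each give a combined false-positive rate well above 0.05. The regression is not independent confirmation, because the same data chose its variables. With 17 pairs, only a large sample correlation can reach significance, so a null or weak association that passes is reported as a substantial one.

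**Working it through.** **The plan's own figure.** The plan states: "A sample size of 17 will provide at least 80% power to detect a clinically significant treatment difference of 1 Borg unit in dyspnea intensity". It assumes "a standard deviation of 1.35 Borg units for the difference between values in a two-treatment crossover study", α = 0.05 and "a two-tailed test of significance". The printed β of 0.8 is read as power. For a paired t-test the noncentrality is 1/(1.35/√17) = 3.05 and the critical t on 16 df is 2.120, which gives power of 81.8%. With n = 16 it is 79.1%. The figure of 17 reproduces and is not in question.

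**Inputs for the screen.** From the plan: 17 patients, 0.05 per test, two-sided, no adjustment. Assumed: the number of candidates m. The t-test paragraph names ten exercise variables as examples (V_E, V_T, breathing frequency, HR, IC, IRV, VO2, VCO2, PETCO2, SpO2), before pressure, EMGdi, resting-function and baseline variables. The Pearson paragraph names only classes, so m = 10 to 30 is shown as a range.

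**Threshold for selection.** |r| = t/√(n − 2 + t²). With n = 17, t = 2.131 on 15 df, so |r| = 2.131/√(15 + 4.543) = 0.48. In simulation, null variables that pass average |r| of about 0.56.

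**Expected false positives, one outcome.** 0.05 × m = 0.5, 1.0 and 1.5 for m = 10, 20 and 30.

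**Chance of at least one.** For independent candidates this is 1 − 0.95^m. For equally correlated candidates it was simulated with n = 17 and no true association.

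| Correlation between candidates | m = 10 | m = 20 | m = 30 |
|---|---|---|---|
| 0 | 40% | 64% | 79% |
| 0.5 | 30% | 44% | 53% |
| 0.7 | 22% | 30% | 36% |

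**More than one dyspnea outcome.** The search also covers qualitative and affective dimensions. Suppose there are four outcomes (intensity, effort, unsatisfied inspiration, unpleasantness; the number is an assumption) that correlate with each other as strongly as the candidates do. The chance runs from 49% (correlation 0.7) to 87% (0) for m = 10, and from 69% to 99.8% for m = 30.

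**The second stage.** In a simulation that screened pooled differences and then refitted each selected variable with treatment and interaction, 72-80% of the chance variables that had passed were again below 0.05. In fresh data about 5-7% were. The refit used ordinary least squares, one variable at a time, and not the planned multivariable model with random subjects. It shows the direction and rough size of the selection effect, not the exact rate for this plan.

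**The case against.** The strongest defence is that the screen is secondary. The objective is a comparison of treatments, and Appendix 4 names change in dyspnea at 4 minutes as the primary endpoint. The link between dyspnea and EMGdi/EMGdi,max is hypothesised in advance, and the treatment comparisons carry Bonferroni. This stands and limits the reach of the point. It does not answer it, because the plan never calls the search exploratory.

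Four stronger readings are tempting, and the documents do not support them.

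- *A false contributor is more likely than not.* For one outcome this holds only with many candidates or weak correlation between them. Some candidates are functions of others: Pdi is the difference between Pga and Pes, and V_E is V_T times breathing frequency. Independence is therefore unrealistic, and at correlation 0.7 the chance is 22-36%. All these figures also assume that no candidate is truly related to dyspnea, whereas the Background reports strong correlations with ventilation and effort.
- *Every selected correlation is inflated.* In simulation at n = 17, a true r of 0.7 averages 0.72 after selection and a true r of 0.8 about 0.80. The inflation matters for null or weak associations: a true r of 0.3 can be selected only if the sample value is at least 0.48 in absolute size.
- *Pooling both treatments creates false contributors.* With 34 rows and treatment means 1 SD apart in both variables, an unrelated variable passes the Pearson test in about 21-23% of simulations. But the plan does not say that it pools, and its regression includes treatment. Only 2.5-4% passed both the screen and a least-squares model with treatment as a covariate. What remains is an ambiguity to settle.
- *The correlations must be Bonferroni-adjusted.* This is a trade-off. With five variables at 0.01 each, the required |r| rises from 0.48 to 0.61, and power for a true r of 0.5 falls from about 56% to about 30%.

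**Conclusion.** The point holds as a weakness of a secondary analysis. An open list is screened at an unadjusted 0.05, and the regression re-uses the data that selected its variables. With one outcome and no true association, the chance of at least one false contributor is about 22-40% for 10 candidates and 36-79% for 30. The lower ends assume inter-candidate correlation of 0.7 and the upper ends independence. The rate is higher if several dyspnea dimensions are screened. The number of candidates, their correlation and the number of outcomes are assumptions, because the plan states none of them.

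A reader might infer that the trial's main conclusions are undermined. They are not: the prespecified EMGdi/EMGdi,max hypothesis, the primary comparison of dyspnea and the sample size of 17 stand apart from this search.

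**What to change.** 1. Name in advance the few variables that the hypothesis implies, for example changes in EMGdi/EMGdi,max, V_E, IC, IRV and the effort-to-V_T ratio. Assess them in the planned model with treatment and subject effects, whatever their Pearson p-value. This also keeps a hypothesised variable from being dropped by the screen, which a true r of 0.5 would pass only about 56% of the time at n = 17.
2. State that correlations are computed within each treatment (17 pairs). Do not treat 34 rows from 17 patients as independent.
3. Report every other variable as r with a 95% CI, labelled exploratory, and do not declare it a contributor because p<0.05.
4. Multiplicity adjustment within the named list is optional, given its cost in power. If it is used, state the family of tests that it covers.

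The cost is analysis wording only: no further patients, visits or measurements. The downside is that fewer variables can be called significant contributors.

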Study design: This will be a single-centre, randomized, double-blind, 2-treatment crossover study evaluating the differential effects of nebulized fentanyl citrate (100µg) and nebulized bronchodilator (0.5mg ipratropium bromide + 2.5mg salbutamol) on exertional dyspnea and physiological responses to a standardized exercise task. After giving written informed consent, participants will complete 5 visits, each conducted in the morning 2-7 days apart [Appendix 4]. Visit 1 (screening): medical history, symptom evaluation, complete pulmonary function testing, a symptom-limited incremental exercise test to determine maximal work rate (Wmax), and familiarization to a new standardized exercise task (4-min cycle exercise test). Visits 2 & 3 (run-in): repeatability of the 4-min cycle exercise test. Visits 4 and 5 (treatment): pre-drug pulmonary function tests (spirometry, plethysmography) and a 4-min cycle exercise test while breathing a gas mixture with a constant fraction of 21% oxygen (room air = 21%) FiO₂); nebulized of either fentanyl or bronchodilator; 30-min post-drug, subjects will perform post-drug pulmonary function tests and a 4-min cycle exercise test while breathing a gas mixture with a constant fraction of 30% oxygen (30% FiO₂) after fentanyl and 21% oxygen (21% FiO₂) after bronchodilator. Exercise tests at Visits 4 and 5 will include detailed measurements of dyspnea (intensity, quality, affective dimensions), EMGdi and pressure-derived respiratory mechanical measurements. Vital signs and systemic side-effects will be monitored. Regularly used inhaled corticosteroids will be permitted as usual throughout the study. Subjects will adhere to the standard withdrawal of bronchodilators prior to each visit: short-acting β_2 -agonists, short-acting anticholinergies, long-acting β_2 -agonists and long-acting anticholinergics will be withdrawn 6, 12, 24 and 24 hours, respectively. Subjects will avoid caffeine, heavy meals, alcohol and major physical exertion prior to visits. Although inhalation of fentanyl citrate has not been associated with significant adverse symptoms or side-effects there is always a possibility that study participants could experience certain side-effects such as drowsiness, sedation and dizziness. As such, participants will be required to have someone accompany them home after their fourth and fifth study visit. If someone is not available to drive them on those days they will be required to take a taxi to and from the lab.

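### The slope-by-treatment test names subject as its only random term, so for predictors that change during exercise its standard error can be too large or too small

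*Combined protocol and SAP*

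**What the plan says.** The last paragraph of Statistical analysis first screens predictors by Pearson correlation, using post-minus-pre differences at 4 minutes. It then plans a multivariable linear regression of dyspnea intensity on the variables that prove significant. Treatment enters as a categorical effect, and "an interaction term will be used to determine whether the relationship was similar across treatments". On random effects it says that "subjects will be treated as random effects to account for serial measurements", with subject nested within treatment. It names no random slope, within-test correlation structure, robust standard error or degrees-of-freedom method. The same section sets the threshold: "A p<0.05 significance level will be used for all statistical analyses".

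The design is a "single-centre, randomized, double-blind, 2-treatment crossover study", so every patient supplies data under both treatments. The exercise-testing section defines measurements at rest, at minutes 1, 2 and 3, and at end-exercise (minute 4), which is five points per test.

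The Background section and Appendix 3 hypothesise that the relation between dyspnea and EMGdi/EMGdi,max is unchanged by either treatment. The Background also reports that the dyspnea-ventilation slope fell after bronchodilator but not after fentanyl.

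**The concern.** The interaction is a difference between two slopes. A random intercept absorbs differences in level between patients, not differences in slope. With 17 patients, two post-dose tests and five points there are 170 observations. Removing 34 subject-within-treatment levels and 2 slopes leaves 170 − 34 − 2 = 134 residual degrees of freedom, yet only 17 patients supply a slope difference.

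Two errors follow, in opposite directions. Slope variation that a patient shows at both visits cancels in the within-patient contrast, but the model leaves it in the residual, so the standard error is too large. Slope variation between a patient's two visits does not cancel, but the model spreads it over 134 degrees of freedom as independent noise, so the standard error is too small.

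This interaction is the plan's only stated test of whether a dyspnea relationship differs between treatments. An inflated standard error favours a non-significant result, which could be read as support for an unaltered EMGdi relationship. A deflated one could produce a false difference in mechanism.

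**Working it through.** **1. The plan's own figure.** The plan states: "A sample size of 17 will provide at least 80% power to detect a clinically significant treatment difference of 1 Borg unit in dyspnea intensity". Its inputs are "a standard deviation of 1.35 Borg units for the difference between values in a two-treatment crossover study" and "α =0.05, β =0.8, and a two-tailed test of significance" (0.8 is evidently the power). For a paired t-test the noncentrality is √17 × 1/1.35 = 3.05 and the critical value on 16 df is 2.120. Power is 81.8% at n = 17 and 79.1% at n = 16, so 17 reproduces. That calculation concerns dyspnea at 4 minutes and says nothing about slopes.

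**2. Formula for the interaction.** Let τ_u be the SD of slopes between patients (same at both visits), τ_w the SD of slopes between visits within a patient, σ the residual SD, and S the sum of squares of the predictor within one test. With equal S in all tests:

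- True variance of the slope difference = (2/17)(σ²/S + τ_w²).
- Expected residual sum of squares around the two common slopes = 134σ² + 32S(τ_u² + τ_w²), because each treatment's 17 slopes contribute 16 df.
- Variance reported by the model = (2/17)[σ²/S + (32/134)(τ_u² + τ_w²)], where 32/134 = 0.239.

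The two agree when slopes do not vary, or when τ_w² = 0.239(τ_u² + τ_w²), which is τ_w = 0.56 τ_u. Below that ratio the test is too conservative; above it, too liberal.

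**3. Inputs.** From the documents: 17 patients, two post-dose tests, five points, a 5% two-sided test. Assumed, because the documents give no values: a predictor running 25, 42, 54, 62, 68 (% of EMGdi,max) with point-to-point SD 3; mean slope 0.10 Borg per unit; residual SD 0.5 or 1.0 Borg. This gives S ≈ 1172.8 + 4 × 9 = 1208.8.

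**4. Numbers in.** With σ = 0.5, σ²/S = 0.25/1208.8 = 0.000207.

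- τ_u = 0.04, τ_w = 0: model SE = √[(2/17)(0.000207 + 0.239 × 0.0016)] = 0.0083; true SD = √[(2/17)(0.000207)] = 0.0049.
- τ_u = 0, τ_w = 0.04: model SE = 0.0083 again; true SD = √[(2/17)(0.000207 + 0.0016)] = 0.0146.

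**5. Simulation.** 2,000 trials per setting with no true slope difference, fitted by REML. The last three columns are false-positive rates at nominal 5%.

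| σ | τ_u | τ_w | Mean model SE | True SD | Planned model | Random intercept for subject only | Paired slopes |
|---|---|---|---|---|---|---|---|
| 0.5 | 0 | 0 | 0.0049 | 0.0047 | 4.3% | 7.9% | 4.8% |
| 0.5 | 0.04 | 0 | 0.0081 | 0.0053 | 0.4% | 1.8% | 4.2% |
| 0.5 | 0 | 0.04 | 0.0082 | 0.0147 | 27.1% | 26.5% | 4.8% |
| 0.5 | 0.04 | 0.02 | 0.0088 | 0.0086 | 4.6% | 9.0% | 5.1% |
| 0.5 | 0.04 | 0.04 | 0.0105 | 0.0148 | 16.5% | 21.4% | 4.6% |
| 1.0 | 0 | 0 | 0.0095 | 0.0095 | 5.2% | 5.9% | 6.0% |
| 1.0 | 0.04 | 0 | 0.0116 | 0.0098 | 2.3% | 3.6% | 5.3% |
| 1.0 | 0 | 0.04 | 0.0116 | 0.0170 | 18.1% | 20.9% | 4.8% |
| 1.0 | 0.04 | 0.02 | 0.0121 | 0.0120 | 4.9% | 7.7% | 4.3% |
| 1.0 | 0.04 | 0.04 | 0.0134 | 0.0172 | 13.9% | 17.1% | 5.5% |

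The simulated errors agree with the formula. Over all 20 settings run (τ_u up to 0.06, τ_w up to 0.04) the planned model ranged from 0.1% to 27.1%, the subject-only intercept from 0.6% to 26.5%, and paired slopes from 4.2% to 6.0%.

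**6. Narrower range.** With τ_u at 0 or 30% of the mean slope and τ_w from 0 to 30%, simulation gives about 1% to 23% at σ = 0.5 and about 3% to 13% at σ = 1.0, against 4.3% to 5.6% for paired slopes. The formula's extremes, from 2Φ(−1.978 × model SE/true SD), are close: 0.5% and 22.2% at σ = 0.5, and 2.6% and 12.4% at σ = 1.0.

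**The case against.** **The text does not say intercept only.** It says subjects are random effects and does not exclude random slopes. A reader might infer that the plan rules them out; it does not. But it names none, and an analyst following the sentence would ordinarily fit a random intercept.

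**The regression may use 4-minute values only.** The preceding correlations do, and then the five-point argument would not apply. However, the sentence justifies the random effect by serial measurements. With one value per patient and treatment, a subject-within-treatment effect could not be separated from the residual. The serial reading is the more natural one, but it remains an assumption.

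**Not every predictor is affected.** Resting lung function and baseline characteristics are constant within a test and have no within-test slope. This stands: the point covers only variables measured during exercise.

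**The size is assumed.** This also stands. The documents give no slope variances, and the residual SD matters: doubling it from 0.5 to 1.0 Borg roughly halves the upper rate, from about 23% to 13%.

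**Crossing subject with treatment would suit the design better.** It would, but the table shows that a random intercept for subject alone fails in both directions too.

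**The analysis is secondary.** True, and its predictors are preselected by significance. It nevertheless addresses the stated mechanistic hypothesis.

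**Conclusion.** The point holds, conditionally. With a random intercept only and serial exercise points, the interaction's standard error can be wrong in either direction for predictors that change during exercise. Under the assumed mean slope of 0.10 Borg per %EMGdi,max and the narrower slope SDs in step 6, the false-positive rate is about 1% to 23% (residual SD 0.5 Borg) or 3% to 13% (residual SD 1.0 Borg).

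A reader might infer that the standard error is always wrong, or that the test always finds too many differences. Neither follows: the rate is near 5% if slopes do not vary, or if between-visit variation is about half the between-patient variation, and it falls below 5% when patients' slopes are stable across visits. The documents do not say which case applies.

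Nor does the problem reach the primary comparison or the sample size. Both rest on a paired comparison of dyspnea at 4 minutes, for which 17 patients reproduces. This is a change that should be made to an important secondary analysis.

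**What to change.** State whether the regression uses all exercise time points and which tests it includes. Then:

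1. For each key time-varying predictor (at least EMGdi/EMGdi,max and ventilation), estimate the slope of dyspnea within each patient and post-dose test. Compare the 17 within-patient slope differences: estimate, 95% confidence interval, and paired t-test on 16 df.
2. In the multivariable model, specify random slopes for patient and for patient-by-treatment, with a small-sample degrees-of-freedom method. If the fit is on a boundary or does not converge, fall back to the paired slope comparison.

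The two are not interchangeable. Five points per test cannot support per-patient regressions on several predictors, and two random-slope terms may be hard to estimate from 17 patients.

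The cost is a change to the analysis text; no new data or patients are needed. There are fewer nominal degrees of freedom (16 rather than 134), and the interval is wider where the planned model is too liberal.
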